The most fundamental and in our view the most important limitation of EEG-BCI is that the system does not provide any assistance when it is not attached to the patient. The few paralyzed people who use an EEG-BCI system on a regular basis in the home (eg Sellers et al. 2010) do so for a few hours at a time. The rest of the time, locked in users have no means of initiating communication. Someone who can generate a sound can ask for attention. Someone who is locked in cannot and has to wait until the caregiver initiates contact. An effective BCI system has to overcome this severe limitation if the goal is to improve the life of

locked-in patients. Only an implant that is permanently operational can offer such an improvement.

Intracranial solutions

Signals recorded *directly* from the brain are significantly more detailed than scalp EEG since electrodes record from their immediate, neuronal, environment (Jacobs and Kahana, 2010). Signal to noise ratio is impressive, allowing for detection of even very local changes in brain activity (Vansteensel et al., 2010; Ramsey et al., 2006). Most in the BCI field will agree that signals recorded directly from the brain are of a much better quality than scalp-EEG. In one recent clinical pilot in the USA, researchers succeeded in decoding imagined movements in paralyzed people with an array of needle electrodes implanted in the cortex (Hochberg et al., 2006, 2012), enabling them to move a cursor across a computer screen. This pilot showed that direct brain signals could be decoded in all 5 patients included. An important drawback is the insertion into the cortex which may induce gliosis which leads to loss of signal after months or years. A new approach is one where electrodes consist of small discs that lie on top of the cortex, measuring from several mm of neuronal tissue without damaging it (Leuthardt et al., 2004). We at the UMC have been conducting research on these electrodes and their potential for BCI, which is described below.

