3. STUDY DESIGN

3.1 Design

This study is a single center interventional pilot study, lasting 5 years. The population consists of five patients of age 18–75 with severe paralysis. It is a pilot study preparing the ground for a larger clinical trial, and has an *adaptive trial design*, where we allow for modifications to be made concurrently (e.g. in/exclusion criteria) or prospectively (e.g. discontinuation following interim evaluation, modification of end-of-study date), in communication with DSMB and METC committee (Thabane et al., 2010). For inclusion, patients need to possess at least one rudimentary form of communication (see inclusion / exclusion criteria [Section 4](#) for more details). Completely locked-in patients may be included, if there is clear indication that they understand the protocol and the risks and want to participate, and if their legal guardian agrees to (and signs for) their participation. Patients of the target population are typically no longer in medical treatment after their condition is stabilized, and may live at home or in a care center. Since they may therefore be difficult to find and reach, recruitment will be performed in various ways ([see Section 4.1 for details](#)). Patients or their caregivers can contact the research team directly, or the research team can contact the caregivers after they have given permission for this to their specialist. Patients will be visited multiple times by the research team, to inform them about the details of the study, to obtain informed consent, to verify the physical and mental abilities of the patient to continue with the procedure and to practice tasks. In addition, an EEG measurement session will be conducted. Results of these EEG recordings will provide information about the neuro-electrical signal features in the low-frequency band (high-frequency band changes cannot be measured reliably with EEG), which may be useful to address secondary objective 2. Notably, the EEG measurements may also take place some time after the electrodes and the device were implanted. [See Section 3.2 for a time line and the sections mentioned therein for details](#).

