8.3.8 Home Use and Data Collection

After the patient is released from the hospital, the home use and data collection period starts. During this period, patients will be trained to control the BCI accurately, and data will be collected for research purposes. Between visits of the research team, patients are allowed to use the BCI system at any time they want for practice or real communication purposes (see [Section 8.3.13](#)). During phase 1 and 2, patients can train using the feedback given by the minidisplay/keypad. During phase 3 and 4, patients can also use the assistive technology device for practice between visits.

About six weeks after the patient was released from the hospital, one of the neurosurgeons or the nurse practitioner will visit the patient for a postsurgical medical checkup.

Raw data from the Activa PC+S is saved continuously (see [Section 8.3.11](#)) to monitor signal characteristics over time (see [Objectives Section 2](#)). A log book will be provided, and the caretakers will be asked to write down everything they consider relevant for the BCI project. Notably, this information will be anecdotal and subjective. It may contribute to the BCI optimization process, but research will not depend on it.

The research team will visit the patient on a regular basis ([Section 15.4](#)). During every visit, the VAS Mood and Motivation will be performed (in case of unreliable communication at the time of inclusion, VAS evaluations can only take place after the patient has reached adequate control with the UNP) and the functioning of the BCI system will be assessed using the information written down by the caretaker in the log, and by consultation of the caretaker and/ or patient. Also, a system checkup is performed using the clinician programmer. Subsequently, several tasks will be performed by the patient for training purposes. If necessary, system adjustments (on the level of feature selection, classification and/ or translation, see IMDD) will be made to optimize BCI performance ([Section 8](#); [Section 8.3.11](#); [Section 8.3.12](#)). In addition, psychological and signal data will be collected for research purposes ([Section 15.4](#)).

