In the first phase the patient is familiarized with the concept of a BCI and controls for the first time a cursor on a screen using changes in brain activity. In the second phase the patient is trained to control the switch(es). The main objective is to decrease the time required to elicit a switch event and to increase the accuracy, i.e. increase the number of hits while decreasing the number of false positives. In the course of phase two, the level of proficiency is tested on a regular basis using a formal test. Once the patient succeeds in this test we conclude that he has a functional switch and has reached Level 1 Proficiency (supervised use, see Phase 2 Supervised BCI Control, below). In the third phase the patient is trained to increase the accuracy even more and to use the switch(es) to control assistive technology in a real life setting (unsupervised use, see Phase 3 Unsupervised BCI Control, below). The goal of phase 3 is to allow the patient to use the switch(es) independently of the researchers. The proficiency of the patient in doing so will be formally tested using a predefined sentence on a regular basis (Level 2 Proficiency). These data will be used to address the Primary Objective (see Section 2). In the last phase the patient is trained on autonomously switching the UNP system from 'stand-by' to 'on' mode and vice versa, without external help.

Frequency of visits by the research team will initially, during Phase 1 and 2, be maximally twice per week for at least 4 weeks, or until 28 weeks after implantation. During the first, second or third week only, depending on the condition of the patient, a maximum of 2 extra visits may be planned for training purposes, in order to quickly familiarize the patient with the system. Once a patient has entered phase 3, visits will initially occur once every 2 weeks, for 12 weeks. Subsequently, visits will occur once every 6 weeks until the end of the study. See Section 15.4A and B for examples of quick and slow scenario's. Notably, the actual scenario will depend on the individual patient's progress, and will probably be intermediate between the examples of Section 15.4. In addition, it may be necessary, when BCI performance suddenly decreases while being in a certain phase, to perform certain tasks from one of the previous phases. In that case, it will be made sure that the burden to the patient is not larger than originally planned.

Phase 1 - familiarization

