In scenarios 2-5, one or more components will remain implanted after the end of the study participation. The parts that remain implanted are subject to Post Marketing Surveillance (PMS). PMS will be achieved through the involvement of Medtronic and the research team. The Permanent extensions, Activa PC + S and Antenna are subject to PMS by Medtronic. The subdural leads, both Resume II leads (model 3587A) and model 0913025 Subdural leads, are subject to PMS by the research team in the form of a Post-Market Clinical Follow-up (PMCF). In scenario 4, the Streaming Unit and Brain Interpreter Software will also be assessed in a PMCF study. The PMS plan is described in the IMDD (see Section D2). After

the end of study participation, the participants remain in the study to conduct the PMCF study (see Post Marketing Clinical FollowUp v2.0), consisting of a yearly questionnaire on adverse events, without further requirements for the patient. Adverse events will be registered as described in Chapter 9. The last informed consent before end of study participation remains valid during the PMCF period. Data obtained after the end of study participation will not be part of the final study report and are not monitored by the DSMB or monitor.

In case of medical costs that need to be made after the end of study participation, that are related to the implant, but not to damage due to study participation, it will be investigated if the health insurance of the participant or the sponsor of the study (UMC Utrecht) will reimburse these costs.

Surgery, scenario 1

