9.2 AEs, SAEs and SUSARs

9.2.1 Adverse events (AEs)

Adverse events are defined as any undesirable experience occurring to a subject during the study, whether or not considered related to the experimental intervention. All adverse events reported spontaneously by the subject or observed by the investigator or his staff will be recorded. All adverse events related to the Medtronic products will be reported to Medtronic.

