11.4.3 Surgery

The experiments involve a surgical procedure with implantation of electrodes underneath the skull, lead wires under the skin from the head to the chest, and/or positioning of a medical device under the skin on the chest. This procedure is the same as for deep-brain stimulators, but with a less invasive electrode positioning as they do not penetrate brain tissue (deep-brain stimulators travel through much of the brain white matter to reach their goal in the thalamus). Medtronic has already delivered 85.000 DBS stimulators for implantation in Parkinson patients alone, indicating that implantation of the device is by now a standard procedure.

* Because electrodes are already in place, imaging, electrode placement surgery and strip selection procedures are not relevant for new participants with existing implant.

The surgical implantation procedures (implantation of the electrodes and implantation of the Activa PC+S device) carry the same risks associated with any other brain surgery. In the worst case, risks of brain surgery may include serious complications such as coma, bleeding inside the brain, seizures and infection. Some of these may be fatal. However, the chance that complications occur is very low, among others since electrodes do not penetrate the cortex. The risk of subdural or epidural hemorrhage ranges from none to 2%. This literature is mostly based on devices penetrating the cortex (Bronstein et al., 2011; Franzini et al., 2011). Once implanted, the system may become infected. The risk of intracranial infection after implantation surgery is around 5% in the literature. The risk of infection at the abdomen where the cables are externalized is likely smaller.

Depending on the severity and the location of the infection, parts of the system may have to be explanted. After implantation, parts may wear through the skin, and the lead or lead/extension connector may move. Any of these situations may require additional surgery.

Notably, having two brain surgeries close together in time is standard clinical practice in the treatment of severe intractable epilepsy and other conditions, and does in itself not add any additional risks.

Risks related to the explantation scenarios ([see Section 8.3.14](#)) include infection (~3%) and, in the case of explantation of all implanted parts (including the electrodes), subdural or epidural hemorrhage (0-2%).

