15.4 Post Implantation Time Line

A. Example of a quick scenario, in which the patient reaches first level of proficiency within 4 weeks after implantation. In this case, the frequency of visits will decrease after 4 weeks, and Phase 3 and Phase 4 training will commence. Note that green and yellow columns are related to BCI performance by the patient, whereas purple, pink and blue are related to data collection for research purposes only. The planning of this research data collection is fixed and independent of the BCI training progress.

B. Example of a slow scenario, in which the patient reaches first level of proficiency just before the critical decision moment at 28 weeks after implantation, after which the frequency of visits will decrease and Phase 3 and Phase 4 training will commence. Note that green and yellow columns are related to BCI performance by the patient, whereas purple, pink and blue are related to data collection for research purposes only. The planning of this research data collection is fixed and independent of the BCI training progress (unless the patient is excluded from further study because of not reaching level 1 proficiency within 28 weeks after implantation, in that case, also data collection for research is terminated at that point).

A

B

Home Use and Data Collection Standard Operating Procedure

Executive summary

This Standard Operating Procedure (SOP) has been designed to support the research team of the UNP project in the safe and correct execution of the study protocol, part 'Home Use and Data Collection'. It describes the procedure during the research visits of members of the research team at the patient's home. If something is unclear, contact the study coordinator.

1. Consult patient and caretaker on functioning of the BCI system
2. Copy updates from the caretaker log
3. Press Patient Button on Streaming Unit to switch off
4. Take off antenna
5. Use the N'Vision Clinician Programmer to check battery level from Start Session screen (Fig 1): Log battery status and voltage

[figure not shown]

Figure 1

6. Use the N'Vision Clinician Programmer to check impedance as follows:
 - 6.1. Access the Measurement menu and select Electrode Impedance.

6.2. Select the Left (hemisphere) tab or the Right (hemisphere) tab (Fig 2).

6.3. Select the Settings button (Fig 3).

[figure not shown]

Figure 2

6.4. Select 0.25V amplitude value from the drop-down list.

6.5. Select Bipolar as electrode configuration option.

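### Section 9.2.1 collects adverse events passively, names no caregiver source and schedules no adverse event question, so events between visits may be under-recorded in people who generally depend on others to start contact

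*Combined protocol and SAP*

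**What the plan says.** Section 9.2.1 defines an adverse event broadly, as any undesirable experience during the study, whether or not related to the intervention. It then gives two routes into the record: "All adverse events reported spontaneously by the subject or observed by the investigator or his staff will be recorded".

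Other passages bear on how this rule would work:

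- **Population.** The introduction says of initiating communication: "Someone who is locked in cannot and has to wait until the caregiver initiates contact". Section 3.1 states the usual requirement: "For inclusion, patients need to possess at least one rudimentary form of communication". The same section, with Section 4.2, also allows people who cannot communicate reliably, given evidence that they wished to take part.
- **Visit procedure.** Step 1 of the home-visit procedure in Section 15.4 is "Consult patient and caretaker on functioning of the BCI system". Later steps cover copying the caretaker log, battery and impedance checks, the mood and motivation scales, parameter settings and tasks. Neither the steps nor the Research Visit Checklist contains an adverse event item.
- **Caretaker log.** Section 8.3.8 asks caretakers to note what they think bears on the BCI project. It calls the content anecdotal and adds: "It may contribute to the BCI optimization process, but research will not depend on it".
- **Visit spacing.** Section 8.3.9: "Once a patient has entered phase 3, visits will initially occur once every 2 weeks, for 12 weeks". After that, visits are six-weekly until the end of the study.
- **Risks after implantation.** Section 11.4.3 includes infection of the system and this: "After implantation, parts may wear through the skin, and the lead or lead/extension connector may move".
- **After participation ends.** Section 8.3.15 does provide an active enquiry, "consisting of a yearly questionnaire on adverse events, without further requirements for the patient".

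**The concern.** A rule based on spontaneous report assumes that the subject can raise a complaint unprompted. This population is largely defined by difficulty in doing so. The people best placed to notice a problem between visits are the caregivers, and 9.2.1 does not list them as a source.

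The protocol recognises this elsewhere. For participants with unreliable communication, caregivers or guardians are consulted on depressive symptoms (8.3.1), on neurological tests that need communication (8.3.2) and on emotional wellbeing (11.4.5). Adverse event collection has no matching provision.

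Adverse event data feed the DSMB's safety analyses (9.5) and the neurosurgeon's advice on what to do with the implant when participation ends (8.3.15). They also inform the larger trial, into which the pilot data may be carried (Section 1). With five participants, one participant whose event goes unrecorded changes an observed proportion by 1/5 = 20 percentage points.

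**Working it through.** The plan states no detection rate or expected adverse event count, so there is no figure to reproduce. The check has two parts.

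**1. Is there any route by which someone is required to ask about, or accept a caregiver's report of, an adverse event during participation?**

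| Contact | Section | Purpose stated | Defined as an adverse event source? |
|---|---|---|---|
| Spontaneous subject report | 9.2.1 | Adverse events | Yes |
| Observation by investigator or staff | 9.2.1 | Adverse events | Yes |
| Consultation of patient and caretaker at visits | 8.3.8, 15.4 step 1 | Functioning of the BCI system | No |
| Caretaker log, copied at visits | 8.3.8, 15.4 step 2 | Matters bearing on the BCI project | No |
| Mood and motivation scales, talks with caretakers | 8.3.8 | Psychological wellbeing | No |
| Battery, impedance and signal checks | 15.4 | System integrity | No |
| Post-operative neurological examination, late one only if needed | 8.3.2 | Change from pre-operative status | No |
| One medical check-up about six weeks after discharge | 8.3.8 | Post-surgical check | No |
| Yearly adverse event questionnaire | 8.3.15 | Adverse events | Yes, but only after participation ends |

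Staff may observe an event at any of these contacts, and 9.2.1 would then have it recorded. None of the contacts during participation requires an adverse event question, and none makes caregiver report a source. For participants without reliable communication, the mood scales are also suspended until they can use the system adequately (8.3.8).

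**2. How long are the intervals on which the passive rule has to operate?**

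Inputs from Sections 8.3.9 and 15.4: phase 3 starts at week 4 after implantation in the quick scenario and week 28 in the slow one. Two-weekly visits then run for 12 weeks, followed by six-weekly visits. The first year is taken as 52 weeks.

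Start of the six-weekly stretch = start of phase 3 + 12 weeks. Length of the stretch = 52 − that start.

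- Quick: 4 + 12 = week 16. 52 − 16 = 36 weeks. 36/52 = 69%. 36/6 = 6 intervals.
- Slow: 28 + 12 = week 40. 52 − 40 = 12 weeks. 12/52 = 23%. 12/6 = 2 intervals.

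Each interval is 6 × 7 = 42 days between routine visits. Section 8.3.9 expects real courses to lie between these examples. Participants who extend beyond 12 months stay on the six-weekly schedule until the end of the study.

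**The case against.** The strongest reply is that the visits are far from blind to health problems. Staff copy the log, speak with patient and caretaker, measure impedance at all electrodes and place equipment over the chest device. Impedance and signal checks could show a lead problem without any report from the patient. Most participants have some communication channel: consent normally requires 38 of 40 correct choices (11.2.2). Those who reach phases 3 and 4 may be able to type a complaint. The early period, when surgical risk is concentrated, includes an inpatient stay, a CT scan and the six-week check-up. All of this stands. It limits the size of the problem, but it does not supply an adverse event question or a caregiver source.

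Three stronger readings are tempting, and the documents do not support them.

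- **Events will be missed because participants cannot report.** The introduction describes the locked-in state in general. Most participants could answer if asked, and staff can observe. The text supports possible under-recording, not certain loss.
- **The surgical risks give the size of the problem.** Section 11.4.3 quotes about 5% for intracranial infection, so a reader might compute 1 − 0.95^5 = 22.6% for at least one case in five. That is the chance that an infection occurs, assuming independence. It is not the chance that one goes unrecorded, and the rate is not given for the later six-weekly period.
- **The two-subject rule in Section 8.7 is undermined.** Let p be the risk of a serious adverse device effect per subject and d the share recorded, with x = p × d. The chance of at least two recorded subjects in five is 1 − (1 − x)^5 − 5x(1 − x)^4. At an assumed p = 0.20 it is 26.3% with d = 1, 16.5% with d = 0.75 and 8.2% with d = 0.50. The documents give neither p nor d. The rule concerns serious effects, for which d is likely to be high, so no material effect is claimed.

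Some material was not available: the separate monitoring plan (12.2), the device dossier and the schedule charts in 15.4. An enquiry could be described there.

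**Conclusion.** The concern holds as a gap in ascertainment. During participation, the protocol defines adverse event collection passively, omits caregivers and guardians as a source, and schedules no enquiry. With routine visits up to 42 days apart for roughly 23% to 69% of the first year, depending on training progress, events between visits may be under-recorded. The exposure is mainly to non-serious, subjective or early-stage events. Events that need admission or surgery are likely to come to notice.

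The extent of under-recording cannot be estimated from the documents. The conclusion assumes that the unseen material contains no adverse event enquiry; if it does, 9.2.1 and 15.4 should point to it. No sample size, error rate or success criterion is affected. This is a cheap improvement to the safety data, not a flaw that threatens the primary endpoint.

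**What to change.** **Section 9.2.1.** Keep the two existing routes and add two more: events reported by the caregiver or legal guardian, and events elicited by a standard open adverse event question put to patient and caregiver at every scheduled and unscheduled visit.

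**Section 15.4.** Extend step 1 of the home-visit procedure with that question, and add one tick box, 'AE enquiry done', to the Research Visit Checklist.

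**Section 8.3.8.** Add an adverse event section to the caretaker log and state that entries in it are source data. The rest of the log can keep its present anecdotal status.

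**Cost.** A few minutes at visits that already take place, a short change to 9.2.1, one checklist line and a log page. No extra visits or staff are needed. More non-serious events will be recorded and will need to be followed under Section 9.4.
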